Appendix II: Symptom Scoring Sheet for Desensitization and Dosage Escalations

- I. Skin:
 - A. Red rash - _____% area involved
 - B. Rash
 - 0 Absent
 - 1 Mild – few areas of redness
 - 2 Moderate – areas of redness, flat and raised rash
 - 3 Severe – large areas of redness (>50%), large amount of raised rash on the body (>25%)
 - C. Itchiness
 - 0 Absent
 - 1 Mild – occasional scratching
 - 2 Moderate – scratching continuous for more than 2 minutes
 - 3 Severe – continuous scratching all over
 - D. Hives/Swelling
 - 0 Absent
 - 1 Mild – less than 3 hives
 - 2 Moderate – greater than 3 but less than 10 hives
 - 3 Severe – Body covered in hives
- II. Upper Respiratory:
 - A. Sneezing/Itching
 - 0 Absent
 - 1 Mild – rare bursts of sneezing, mouth itching
 - 2 Moderate – less than 10 bursts of sneezing, sometimes rubbing of nose and/or eyes, mouth itching lasting longer than 10 min.
 - 3 Severe – continuous rubbing of nose and/or eyes, swelling around the eyes and/or sneezing often, swelling in or around the mouth
 - B. Stuffy nose
 - 0 Absent
 - 1 Mild – small amount of trouble breathing through the nose
 - 2 Moderate – nose feels stuffy; breathes through mouth most of the time
 - 3 Severe – nose runs freely despite sniffing and tissues
 - C. Runny nose
 - 0 Absent
 - 1 Mild – sniffing sometimes
 - 2 Moderate – sniffing often and need tissues
 - 3 Severe – nose runs freely despite sniffing and tissues
 - D. Throat symptoms
 - 0 Absent
 - 1 Mild – throat clearing, cough
 - 2 Moderate – hoarseness, frequent dry cough
 - 3 Severe – Breathing causes loud, squeaky sounds

- III. Chest:
 - A. Wheezing
 - 0 Absent
 - 1 Mild – wheezing only heard when examined by physician
 - 2 Moderate wheezing from breathing in and out
 - 3 Severe – shortness of breath, use of chest muscles to breath, and wheezing

- IV. Abdomen:
 - A. Subjective complaints
 - 0 Absent
 - 1 Mild – complaints of nausea or abdominal pain, no change of activity
 - 2 Moderate – frequent complaints of nausea or pain, decreased activity
 - 3 Severe – patient in bed; crying or notably distressed
 - B. Objective complaints
 - 0 Absent
 - 1 Mild – 1 episode of emesis or diarrhea
 - 2 Moderate – 2 to 3 episodes of emesis or diarrhea or 1 of each
 - 3 Severe- more than 3 episodes of emesis or diarrhea or greater than 1 of each

Algorithm for Dose Adjustment Based on Symptoms:

- A. For a Grade 1 reaction, the daily dose will be continued until the next visit. If a subsequent Grade 1 or greater reaction occurs, the participant will hold future doses and return to the clinic within 48 hours and be challenged to the previous tolerated dose.
- B. For a Grade 2 and 3 reaction, the participant will hold all future doses and return to the clinic within 48 hours to be challenged to the previous tolerated dose. If a Grade 3 reaction occurs greater than 2 times, the participant's dose will remain at the highest tolerated dose and will enter the maintenance phase of the study.
- C. Grade 4 reaction will cause discontinuation of the study for that patient and the patient will be given the option to be converted to a peanut equivalent dose.

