The process of desensitization through immunotherapy occurs after an initial food challenge to determine what amount of food allergen causes a clinical reaction in the subject. There are two phases in treatment with oral immunotherapy. In the first phase, the build-up phase, the subject ingests gradually escalating doses of peanut flour, administered orally in a vehicle once every day with weekly or bi-weekly dose escalation. Once a maintenance dose has been achieved, the subject continues to take this amount in a peanut equivalent dose over a period of years. Peanut equivalent dosing has been used in several prior peanut OIT trials without report of increased side effects or adverse events. (17-20) The peanut flour manufacturer for the initial trials in peanut oral immunotherapy by centers in the Consortium of Food Allergy Research (CoFAR) only provided dosing for the buildup phase for the trials and peanut equivalent dosing was used by centers for the maintenance phase. (Personal communication) Therefore, given the experience with peanut equivalent dosing, after the first year of this study, patients will be switched to a daily peanut equivalent dose and intake will be monitored by daily diaries. Since the daily dose will still be 3900 mg of peanut protein for the maintenance phase, the immunologic effects of the peanut dosing are not likely to be affected. (11, 12)

An open label study with an initial dose of 100 µg increased to 300 mg maintenance dose for several months demonstrated efficacy in over 90% of the subjects with desensitization and tolerance of a 3900 mg dose on food challenge.(11,12) A follow up double blind study

demonstrated efficacy with treated subjects tolerating 5000 mg compared to 280 mg in placebo subjects. The safety analysis of these studies demonstrated that 93% of children experienced symptoms on initial dosing day with 15% requiring epinephrine.(9) Most reactions were mild. However, when the initial dose was decreased from 50 mg down to 6 mg, allergic side effects were noted in only 47%. Of 10,184 home maintenance dosings of peanut flour, only 3.5% caused symptoms, with 2 subjects receiving epinephrine, each after one maintenance dose (0.02%). The relative safety of this approach has been demonstrated in these initial trials.(9)

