Appendix III: Instructions for Daily Home Doses

Subject ID: _____

Date: / / _____

Important: We require that you please carry with you 2 epinephrine auto-injector devices at all times and must demonstrate to the investigators the correct use of the epinephrine auto-injector. Failure to consistently carry an epinephrine auto-injector constitutes grounds for termination from the study. If you do not have an epinephrine auto-injector on your person, your appointment(s) will be rescheduled.

- Take one dose per day, preferably at the same time every day. Prior to taking the dose, you must eat a snack high in carbohydrate and fat (example: bagel, chips) then eat the peanut flour mixed in a small amount of liquid (example: less than 1 tablespoon (15 ml) of water, apple juice etc.) or mixed into another food (example: less than one half of a cup (8 tablespoons) of apple sauce, ice cream). Liquid or semi-solid foods can be mixed with the dose to facilitate consumption.

After eating the flour, your child must be with a supervising adult for the next 2 hours so they can monitor for any possible reaction. Your child cannot go to school, go to bed, or take hot showers within 2 hours of eating the peanut flour. No strenuous physical activity during the observation period.

- Travel
 - No international traveling is allowed
 - Domestic Traveling within the continental U.S.
 - Take dose at the same time as place of origin (i.e. dose time in Houston 4pm, then take the dose at 4pm final destination)
 - No traveling on cruise ships
- Please ensure that the vehicle food that the peanut flour is mixed with is not food that your child is allergic to.
- Record any symptoms occurring within 2 hours of taking the daily dose.

Symptoms to look for:
Mild Symptoms (itching, mild flushing, sneezing, nasal congestion, eye itching, swelling of lips, hives/swelling in one or two areas of the body, nausea)
Moderate to Severe Symptoms (hives/swelling all over the body, shortness of breath, cough, chest tightness, vomiting, abdominal pain, feeling of tightness around the throat, feeling faint, skin

turning blue, and breathing with loud, squeaky sounds)

- Please use the Allergic Reaction Treatment Plan as a guide during an allergic reaction.
- Call and inform the research team of any reaction (even mild cases) and make an appointment to see the research team for the following day.

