Appendix VI: Peanut Oral Immunotherapy – Safety Checklist

Subject ID: _____ **Date:** ___/___/____

Please initial each line and sign/date at the bottom.

_____ I acknowledge that Caregiver understands the safety risks and implications of this study.

_____ Caregiver received training and understand how to use an Epinephrine injector.

_____ Caregiver received training and understands the signs and symptoms of an allergic reaction.

_____ Caregiver received training and understands when to give Benadryl, when to use an Epinephrine injector, and when to call 9-1-1.

_____ Caregiver understands the need to have their unexpired Epinephrine injector with them at all times.

_____ Caregiver/ understands that if Epinephrine injector is not with them during a research related appointment, then that appointment will be canceled and rescheduled.

_____ Caregiver understands that they will need to come to Texas Children’s Hospital every two weeks for the first year of the study, then every 6 months for the last two years of the study to receive their daily peanut doses.

_____ Caregiver understands that they must notify the research team of any allergic reactions, even mild cases, on the day the reaction occurs.

_____ Caregiver understands that they must call 9-1-1 for severe reactions and to obtain further medication attention.

_____ Caregiver understands that they will need to come to Texas Children’s Hospital the next day if a reaction occurs at home.

_____ Caregiver understands that his/her child will need supervision 2 hours after taking their daily peanut dose at home.

_____ Caregiver understands that his/her child cannot go to school within 2 hours of eating the peanut flour and cannot go to bed within 2 hours of eating the peanut flour.

_____ Caregiver received a contact list of phone and pager numbers from research team and I know who to call if my child experiences an allergic reaction.

_____ Caregiver understand that the peanut flour needs to be stored in a refrigerator with the container lids tightly closed.

_____ Caregiver understand that if his/her child misses 3-4 doses of peanut flour, they will have to come to Texas Children's Hospital to receive their next scheduled dose.

Investigator or designee Signature: _____

Date: / / _____

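### Appendix II and the family instructions conflict on a first Grade 1 home reaction, and the visible family sheets omit the dose hold that Appendix II requires after repeat or Grade 2–3 reactions

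*Combined protocol and SAP*

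**What the plan says.** The dose-adjustment algorithm at the end of Appendix II is graded.

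- First Grade 1 reaction: "For a Grade 1 reaction, the daily dose will be continued until the next visit".
- Repeat reaction: "If a subsequent Grade 1 or greater reaction occurs, the participant will hold future doses and return to the clinic within 48 hours", followed by a challenge to the last tolerated dose.
- Higher grade: "For a Grade 2 and 3 reaction, the participant will hold all future doses and return to the clinic within 48 hours", again with a challenge.
- Grade 4: discontinuation.

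The documents given to families have no such tiers. Appendix III (flour phase) instructs: "Call and inform the research team of any reaction (even mild cases) and make an appointment to see the research team for the following day". Appendix VIII (peanut-equivalent phase) repeats this. In the Appendix VI checklist, the caregiver accepts coming to the hospital "the next day if a reaction occurs at home", with no limit by grade, and also accepts notifying the team of any reaction on the day it occurs. An investigator or designee signs that checklist.

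Section 1 names safety as the primary outcome. Section 9.2.1 measures the primary objective partly through recorded daily symptoms. Section 7 has symptoms entered in a daily home diary that is reviewed at up-dosing visits.

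**The concern.** The same mild reaction at home leads to different actions depending on which page is followed. Under Appendix II the child keeps dosing and is seen at the next visit, about two weeks away on the Table 3 schedule. Under the family documents the child is seen the next day.

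A second gap concerns the dose itself. After a repeat or Grade 2–3 reaction, Appendix II stops home dosing until the child has been challenged in clinic. The visible text of Appendices III and VIII says to take one dose a day. For up to two missed days it says to carry on as scheduled, with no exception for doses held because of a reaction.

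Two things are at stake. One is that reactions are managed in a uniform and predictable way. The other is the primary safety data, because whether a reaction leads to a clinic assessment or a held dose would depend on the page followed as well as on the reaction.

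**Working it through.** The plan states no figure on this point, so the main check is a side-by-side reading.

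| Reaction at home | Appendix II: seen | Appendix II: next dose | III, VI, VIII: seen | III, VIII visible text: next dose |
|---|---|---|---|---|
| First Grade 1 | next visit | continued | following day | no hold stated |
| Subsequent Grade 1 or greater | within 48 hours | held | following day | no hold stated |
| Grade 2 or 3 | within 48 hours | held | following day | no hold stated |

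**Row 1** conflicts on timing. Taking the next visit to mean the next-day visit fits poorly: Appendix II sets out early return separately, for repeat and higher-grade reactions. On that reading a first mild reaction would be seen sooner than a worse one has to be.

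**Rows 2 and 3** do not conflict on timing, because a visit the following day falls within 48 hours. They differ on the hold.

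**Scale, for illustration only.** Inputs:

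- Section 1, on earlier studies: "Of 10,184 home maintenance dosings of peanut flour, only 3.5% caused symptoms".
- Table 3: two-week steps over 50 weeks, so 25 intervals of 14 doses (350 doses) for a child starting at the lowest dose. Children starting higher have fewer.
- Section 6.5: 24 months of maintenance, about 730 doses, with visits every 6 months (4 intervals of about 182 doses).
- Assumptions: the 3.5% rate applies to every home dose here, doses are independent, and every reaction is Grade 1.

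Probability of at least one symptomatic dose in a 14-dose interval = 1 − (1 − p)^14:

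- p = 1%: 1 − 0.99^14 = 0.13
- p = 3.5%: 1 − 0.965^14 = 0.39
- p = 5%: 1 − 0.95^14 = 0.51

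The number of occasions per child on which the two sources differ depends on what *subsequent* counts from, which Appendix II does not say. At p = 3.5%:

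- Counted once over the whole trial: about 1.
- Restarted at each scheduled visit: 25 × 0.393 = 9.8 in build-up. If Appendix II also governs maintenance, 4 × 1.0 = 4 more, so about 14 in all.
- Restarted also at each return visit: the expected number per interval of n doses is half of [np + P(odd count)], with P(odd count) = [1 − (1 − 2p)^n]/2. For n = 14 this is (0.49 + 0.32)/2 = 0.40, or about 10 over 25 intervals. For n = 182.5 it is (6.39 + 0.50)/2 = 3.44, or about 14 over 4 intervals. The total is about 24.

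**The case against.** The strongest reply is that the algorithm is for staff, the sheets are for families, and same-day notification joins them. Dosing is once a day at about the same time, so staff should normally hear of a reaction before the next dose and can tell the family to hold or continue. The sheets also refer to an Allergic Reaction Treatment Plan that is not visible and may contain a hold. This weakens any claim that a dose due to be held will in fact be taken. It does not settle the first Grade 1 case: staff who consult Appendix II find one answer, and the checklist they sign gives another.

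A second reply is that Appendix II is titled for desensitization and dosage escalations, and that rule B sends some children on to maintenance, so it may govern build-up only. That is a fair reading. The maintenance part of the conflict is therefore conditional.

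A reader might infer three stronger claims that the documents do not support:

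- **That there are three rival rules.** Continuing, and holding with return within 48 hours, are tiers of one algorithm for different events. The conflict is between two sources.
- **That mild reactions will be under-reported.** A next-day visit for every mild symptom may discourage recording, with families living up to 175 miles away (section 3.2). No passage shows that it does, 175 miles is a limit and not a typical distance, and the daily diary and same-day notification work against it. The diary is kept by the same families, so the possibility is not removed.
- **That every symptomatic dose is an extra visit caused by the conflict.** At 3.5%, 0.035 × 1,080 = 37.8 per child describes the burden of the next-day rule read literally. It is not the difference between the rules, because Appendix II also brings children back for subsequent Grade 1 reactions.

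**Conclusion.** The contradiction stands for a first Grade 1 home reaction in build-up, and extends to maintenance if Appendix II applies there. For repeat and Grade 2–3 reactions the timing agrees. What remains is that Appendix II holds doses while the visible family text is silent, subject to the treatment plan that cannot be seen.

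The size cannot be fixed from the documents. Under the stated assumptions the sources would differ for a given child between about once and about 24 times, depending mainly on how a subsequent reaction is counted and whether maintenance is included; other symptom rates would shift these figures. This measures inconsistent handling. It is not an estimate of harm or of reporting bias. The point should be corrected because the primary outcome is safety and the correction is cheap. Which response is clinically right is not judged here.

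**What to change.** Reconcile the passages into one reaction-response rule. For each reaction category and study phase it should state when the child is seen and whether the next dose is held. It should say what a subsequent reaction is counted from, whether the Appendix II algorithm applies in maintenance, and how the family sheets' symptom groups (mild; moderate to severe) correspond to the grades. Use the same wording in Appendices II, III, VI and VIII, and check the Allergic Reaction Treatment Plan and the missed-dose boxes against it. The sponsor decides the clinical content.

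State also that diary entry and same-day notification apply to every symptom whether or not a visit follows. Much of this is already present in section 7 and Appendices VI and VIII; the addition is to separate recording explicitly from attendance.

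The cost is rewording four appendices and re-issuing the home sheets and checklist. No added staff or data collection is needed for the wording itself.

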Appendix III: Instructions for Daily Home Doses

Subject ID: _____

Date: / / _____

Important: We require that you please carry with you 2 epinephrine auto-injector devices at all times and must demonstrate to the investigators the correct use of the epinephrine auto-injector. Failure to consistently carry an epinephrine auto-injector constitutes grounds for termination from the study. If you do not have an epinephrine auto-injector on your person, your appointment(s) will be rescheduled.

- Take one dose per day, preferably at the same time every day. Prior to taking the dose, you must eat a snack high in carbohydrate and fat (example: bagel, chips) then eat the peanut flour mixed in a small amount of liquid (example: less than 1 tablespoon (15 ml) of water, apple juice etc.) or mixed into another food (example: less than one half of a cup (8 tablespoons) of apple sauce, ice cream). Liquid or semi-solid foods can be mixed with the dose to facilitate consumption.

After eating the flour, your child must be with a supervising adult for the next 2 hours so they can monitor for any possible reaction. Your child cannot go to school, go to bed, or take hot showers within 2 hours of eating the peanut flour. No strenuous physical activity during the observation period.

- Travel
 - No international traveling is allowed
 - Domestic Traveling within the continental U.S.
 - Take dose at the same time as place of origin (i.e. dose time in Houston 4pm, then take the dose at 4pm final destination)
 - No traveling on cruise ships
- Please ensure that the vehicle food that the peanut flour is mixed with is not food that your child is allergic to.
- Record any symptoms occurring within 2 hours of taking the daily dose.

Symptoms to look for:
Mild Symptoms (itching, mild flushing, sneezing, nasal congestion, eye itching, swelling of lips, hives/swelling in one or two areas of the body, nausea)
Moderate to Severe Symptoms (hives/swelling all over the body, shortness of breath, cough, chest tightness, vomiting, abdominal pain, feeling of tightness around the throat, feeling faint, skin

turning blue, and breathing with loud, squeaky sounds)

- Please use the Allergic Reaction Treatment Plan as a guide during an allergic reaction.
- Call and inform the research team of any reaction (even mild cases) and make an appointment to see the research team for the following day.
- Please call 9-1-1 for severe reactions (example: confusion, loss of consciousness/non-responsive, collapse, incontinence, bluish skin, feeling faint).

If a daily dose is missed:

- Up to 2 days, continue doses as scheduled.
- 3-4 days after missed dose; repeat previous doses but this dose will be given at Texas Children's Hospital.
- More than 4 days after missed dose, you/your child will return to Texas Children's Hospital for a graded challenge.

[figure not shown]
- Please store peanut flour doses in refrigerator with the container lid tightly closed.

APPENDIX IV:

[figure not shown]
Subject ID: _____

Date: / / _____

[figure not shown]
How to Use EpiPen Auto-Injector Step-by-Step instructions
(www.epipen.com)

1 Form fist around EpiPen® and PULL OFF BLUE SAFETY RELEASE.

2 PLACE ORANGE END against outer mid-thigh (with or without clothing).

3 PUSH DOWN HARD until a click is heard or felt and hold in place for 10 seconds.

4 REMOVE EpiPen®. Massage injection site for 10 seconds.

Source: <http://kidshealth.schn.health.nsw.gov.au/fact-sheets/epipen-use>

1. Prepare the EpiPen or EpiPen Jr Auto-Injector for Injection

- Remove the auto-injector from the clear carrier tube. Flip open the yellow cap of your EpiPen or the green cap of your EpiPen Jr Auto-Injector carrier tube. Tip and slide the auto-injector out of the carrier tube.
- Grasp the auto-injector in your fist with the orange tip pointing downward.
- With your other hand, remove the blue safety release by pulling straight up without bending or twisting it.
Note: The needle comes out of the orange tip.
- Never put your thumb, fingers or hand over the orange tip.

2. Administer the EpiPen or EpiPen Jr Auto-Injector

Hold the auto-injector with orange tip near the outer thigh. Swing and firmly push the orange tip against the outer thigh until it “clicks”. Keep the auto-injector firmly pushed against the thigh at a 90° angle (perpendicular) to the thigh. Hold firmly against the thigh for approximately 10 seconds to deliver the drug. The injection is now complete.

3. Finalize the Injection Process

Remove the auto-injector from the thigh. The orange tip will extend to cover the needle. Massage the injection area for 10 seconds. Get emergency medical help right away. You may need further medical attention. You may need a second EpiPen or EpiPen Jr Auto-Injector should symptoms persist or recur.

Note: Take your used auto-injector with you when you go to see the health care provider.

- Tell the health care provider that you have received an injection of epinephrine. Show the health care provider where you received the injection.
- Give your used EpiPen or EpiPen Jr Auto-Injector to a health care provider for inspection and proper disposal.
- Ask for a refill, if needed.
- The used auto-injector with extended needle cover will not fit in the carrier tube.

